## 10.8 Resistance Analyses

For all subjects, full length NS3/4A and NS5A from baseline samples will be sequenced by next generation sequencing (NGS). For subjects who experience virologic failure (on-treatment virologic failure or post-treatment relapse as defined in Section 10.1), full length NS3/4A and NS5A from the first sample after virologic failure with HCV RNA

$\geq 1000$  IU/mL will be sequenced by NGS. Subjects treated with study drug who do not achieve SVR12 due to reasons other than virologic failure (i.e., prematurely discontinued study drug with no on-treatment virologic failure, HCV reinfection, missing SVR12 data or other reasons as described in Section 10.1, Reasons for SVR12 Non-Response), but have a time point with HCV RNA  $\geq 1000$  IU/mL after treatment discontinuation, will have the sample at that time point sequenced.

Only samples with an HCV RNA level of  $\geq 1000$  IU/mL will undergo sequence analysis in order to allow accurate assessment of products of amplification. Therefore, if the HCV RNA level at the time of HCV virologic failure or treatment discontinuation is  $< 1000$  IU/mL, the sample closest in time after HCV virologic failure/treatment discontinuation with an HCV RNA level  $\geq 1000$  IU/mL will be used.

For each DAA target, signature amino acid positions and a key subset of amino acid positions for the respective inhibitor class are listed in Table 8. Appropriate subtype-specific prototypic reference sequence will be used for comparison with sequences from samples.

**Table 8. Signature Amino Acid Positions and the Key Subset of Amino Acid Positions**

Target	Signature Amino Acid Positions	Key Subset of Amino Acid Positions
GT1 NS3	36, 43 (GT1a only), 54, 55, 56, 80, 107, 122, 132 (GT1a only), 155, 156, 158, 168, 170, 175 (GT1b only)	155, 156, 168 (all GTs)
GT2, 3, 4, 5, 6 NS3	36, 43, 54, 55, 56, 80, 155, 156, 166 (GT3-only), 168	
GT1 NS5A	24, 28, 29, 30, 31, 32, 54 (GT1b only), 58, 62, 92, 93	24, 28, 30, 31, 58, 92, 93 (all GTs)
GT2, 3, 4, 5, 6 NS5A	24, 28, 29, 30, 31, 32, 58, 92, 93	

Included time points for analyses on samples from subjects who do not achieve SVR12 are 1) the sample closest in time after failure/discontinuation with an HCV RNA level of  $\geq 1000$  IU/mL, and 2) 24 weeks post-DAA treatment, provided that resistance-associated

variants were detected by NGS at the time of HCV virologic failure/treatment discontinuation.

The following definitions will be used in the resistance analyses:

- Baseline polymorphism: a polymorphism by NGS in a baseline sample ( $\geq 2\%$  or  $\geq 15\%$  prevalence within a subject's viral population depending on polymorphism frequency threshold utilized) that was not present in the appropriate prototypic reference amino acid sequence for a given DAA target (NS3/4A or NS5A).
- Polymorphism/substitution at a signature amino acid position: polymorphism (relative to reference) present in a baseline sample or substitution (relative to baseline) present in post-baseline sample at a signature amino acid position.
- Post-baseline substitution: an amino acid substitution in a post-baseline time point sample that was not detected at baseline ( $< 2\%$ ) in the subject and is detectable in  $\geq 2\%$  of the sequences from the post-baseline sample.
- Enriched polymorphism: polymorphism present in both the baseline and a post-baseline sample whose prevalence in the post-baseline sample is at least 20 percentage points greater than the prevalence in the baseline sample [(post-baseline % – baseline %)  $\geq 20$ ]
- Treatment-emergent substitution: A post-baseline substitution or an enriched polymorphism.

**Analysis 1:** The following analyses will be provided for all subjects, separated by Arm, HCV subtype, and treatment experience (treatment-naïve or treatment-experienced, and overall):

- A listing of all subjects with baseline polymorphisms (2% detection threshold) at signature amino acid positions for each DAA target (NS3/4A and NS5A).
- A listing of all subjects with baseline polymorphisms (15% detection threshold) at non-signature amino acid positions for each DAA target (NS3/4A and NS5A) for subjects who experience virologic failure.

- A by-subject listing of baseline polymorphisms (15% detection threshold) at signature amino acid positions in subjects with polymorphisms across both NS3 and NS5A, or those with multiple baseline polymorphisms within any one target (NS3/4A or NS5A).
- The number and percentage of subjects with baseline polymorphisms at signature amino acid positions at detection thresholds of 2% and 15%.
- Total number and percentage of subjects with baseline polymorphisms at a key subset of amino acid positions in NS3 only, in NS5A only, any in NS3, any in NS5A, any in NS3 or NS5A, any in NS3 + NS5A, by subtype, and total (include all subtypes).

**Analysis 2:** The impact of baseline polymorphisms on treatment outcome will be assessed as follows: for each polymorphism, the SVR12 rate will be calculated for subjects with and without the polymorphism and the 2 rates will be compared. Analysis will be grouped by Arm, HCV subtype, treatment experience (treatment-naïve or treatment-experienced, and overall), and DAA target (NS3/4A or NS5A).

The following will be included in the analyses of impact of baseline polymorphisms on treatment outcome:

- For each signature amino acid position, presence of any polymorphism at that position (vs no polymorphism at that position), using detection thresholds of both 2% and 15%.
- Each individual polymorphism at each signature amino acid position (vs not that polymorphism) using detection thresholds of 2% and 15%.
- Polymorphisms at each non-signature amino acid position at a detection threshold of 15%.

**Analysis 3:** In subjects with or without polymorphisms in NS3 only, in NS5A only, any in NS3, any in NS5A, any in NS3 or NS5A, any in NS3 + NS5A at the key subset of amino acid positions at 15% detection threshold, the SVR12 rate will be calculated, and the rates with or without polymorphisms will be compared using Fisher's exact test.

Analysis will be separated by Arm, HCV subtype, treatment experience (treatment-naïve or treatment-experienced, and overall). The following tables will be provided:

- Comparison of SVR12 rates by subtype, and total (include all subtypes)
- Comparison of SVR12 rates by genotype, and total (include all subtypes)

**Analysis 4:** The following analyses will be performed for subjects who do not achieve SVR12 or SVR24, and who have post-baseline resistance data available:

- Listings by subject of all treatment-emergent substitutions relative to the baseline amino acid sequences will be provided for each DAA target (NS3/4A and NS5A).
- Listings by subject and time point of all post-baseline substitution at signature amino acid position relative to the baseline amino acid sequence will be provided for each DAA target (NS3/4A and NS5A).
- The persistence of post-baseline substitutions at signature amino acid positions for each target will be assessed by NGS at Post-Treatment Week 24. A listing by subject and time point of all post-baseline substitutions relative to the baseline amino acid sequence will be provided for each DAA target. If resistance-associated substitutions are not detected in a given target for a subject at the time of failure/discontinuation, then that target may not be sequenced in subsequent samples from that subject.

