## **6.3 Missing Data Imputation**

### **Missing Data Imputation for SVR**

HCV RNA values will be selected for analysis based on the analysis windows defined in Section 6.2.

For analyses of SVR, subjects missing visit values will have backward imputation applied, if possible. For backward imputation, if the nearest HCV RNA value after the SVR window is unquantifiable or undetectable, then it will be used to impute the HCV RNA value in the SVR window. If a subject is missing an HCV RNA value within the appropriate SVR window after performing backward imputation, then this value will be imputed with an HCV RNA value from a local laboratory if present; otherwise, the HCV RNA value will be missing. Subjects with missing HCV RNA data in the analysis window, after imputations, will be imputed as a failure.

Regardless of the imputation method described above, if a subject starts another treatment for HCV, then all HCV RNA values for this subject measured on or after the start date of the new HCV treatment will be excluded from analyses. The subject will be considered a failure for summaries of viral response at all time points after the start of the new HCV treatment.

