## **10.0 Efficacy Analysis**

### **10.1 General Considerations**

#### **General Considerations**

All efficacy analyses will be performed on the ITT population, unless otherwise specified.

Missing data will be imputed as described in Section 6.3 for analyses of the HCV RNA endpoints of SVR.

Plasma HCV RNA levels will be determined for each sample collected by the central laboratory using the Roche COBAS® AmpliPrep/COBAS® TaqMan® HCV Quantitative Test, v2.0. The lower limit of detection (LLOD) and lower limit of quantification (LLOQ) for this assay (regardless of genotype) are both 15 IU/mL.

HCV RNA results that are detectable but not quantifiable are reported as "< 15 IU/ML HCV RNA DETECTED" and those that are undetectable are reported as "HCV RNA NOT DETECTED" in the database.

The notation "HCV RNA < LLOQ" is used to represent all HCV RNA values < 15 IU/mL, including values reported as "HCV RNA NOT DETECTED" or "< 15 IU/ML HCV RNA DETECTED." HCV RNA  $\geq$  LLOQ are all quantifiable values of 15 IU/mL or greater.

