### **Definitions for Efficacy Endpoints**

A confirmed quantifiable value during treatment is defined as any two consecutive HCV RNA measurements  $\geq$  LLOQ (or 100 IU/mL for **Breakthrough**), either both during treatment or at the final treatment measurement and the next consecutive post-treatment measurement. A confirmed quantifiable post-treatment value is defined as any two consecutive post-treatment HCV RNA measurements  $\geq$  LLOQ.

**Breakthrough** = confirmed HCV RNA  $\geq$  100 IU/mL after HCV RNA < LLOQ during the Treatment Period; or confirmed increase from nadir in HCV RNA (two consecutive HCV RNA measurements  $>$  1 log10 IU/mL above nadir) at any time point during the Treatment Period. A single breakthrough value ( $\geq$  100 IU/mL or  $>$  1 log10 above nadir) followed by lost to follow-up also will be considered a breakthrough (i.e., will not require confirmation).

**EOT failure** = HCV RNA  $\geq$  LLOQ at end of treatment with at least 6 weeks of treatment, where the HCV RNA value must be collected on or after Study Drug Day 36 and study drug duration  $\geq$  36 days.

**On-treatment virologic failure = Breakthrough or EOT failure;** if a subject meets both definitions of Breakthrough and EOT failure, he or she will be categorized as Breakthrough only.

**SVR4** = HCV RNA < LLOQ in the SVR4 window (4 weeks after the last actual dose of active study drug) without any confirmed quantifiable ( $\geq$  LLOQ) post-treatment value before or during that SVR window.

**SVR12** = HCV RNA < LLOQ in the SVR12 window (12 weeks after the last actual dose of active study drug) without any confirmed quantifiable ( $\geq$  LLOQ) post-treatment value before or during that SVR window.

**SVR24** = HCV RNA < LLOQ in the SVR24 window (24 weeks after the last actual dose of active study drug) without any confirmed quantifiable ( $\geq$  LLOQ) post-treatment value before or during that SVR window.

**Relapse12** = confirmed HCV RNA  $\geq$  LLOQ between end of treatment and 12 weeks after last actual dose of active study drug (up to and including the SVR12 window) for a subject with HCV RNA < LLOQ at Final Treatment Visit who completed treatment, excluding reinfection as described below.

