### **Reasons for SVR12 Non-Response**

Subjects who do not achieve SVR12 (SVR12 non-responders) will be categorized as having:

1. On-treatment virologic failure (see **On-treatment virologic failure** definition);
2. HCV reinfection (see definition described earlier);
3. Relapse12;

4. Prematurely discontinued study drug with no on-treatment virologic failure (defined as any SVR12 non-responder who prematurely discontinued study drug [study drug duration < 52 days for Arm A, < 77 days for Arm B, and < 103 days for Arm C] and did not meet the **On-treatment virologic failure or reinfection** definitions);
5. Missing follow-up data in the SVR12 window (defined as any subject who completed study drug without data in the SVR12 window after applying the imputation rules and not meeting the definitions of [1], [2], [3], or [4]);
6. Other (defined as any SVR12 non-responder not meeting the definitions of [1] – [5]).

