**Table 9. Amino Acid Positions for Subgroup Analysis**

Target	Genotype	Subgroup Amino Acid Positions (All Variants at These Positions are to Be Included)
NS3/4A	1, 2, 3, 4, 5, 6	155, 156, 168
NS5A	1a	28, 30, 31, 93, H58D, E62A
	1b	31, 93
	2	24, 28, 30, 92, 93
	3	24, 28, 30, 31, 58, 93
	4	24, 28, 30, 31, 93
	5	24, 28, 30, 31, 58, 92, 93
	6	24, 28, 30, 31, 58, 92, 93

The number and percentage of subjects in the ITT and mITT-VF populations will be summarized for the presence of baseline resistance- associated variants of:

1. Any NS3/4A variant at baseline (yes/no);
2. Any NS5A variant at baseline (yes/no);
3. Any NS3/4A variant at baseline **or** any NS5A variant at baseline (yes/no);
4. Both NS3/4A and NS5A variant at baseline (i.e., any NS3/4A variant at baseline and any NS5A variant at baseline) (yes/no);
5. Presence or absence of any variant
  - 5a. Any NS3/4A variant at baseline only (i.e., without baseline NS5A variants);
  - 5b. Any NS5A variant at baseline only (i.e., without baseline NS3/4A variants);
  - 5c. Both NS3/4A and NS5A variant at baseline;
  - 5d. None (i.e., no baseline variant in either NS3/4A or in NS5A at baseline).

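### Resistance Analyses 2 and 3 compare SVR12 by baseline polymorphism in ITT only; adding mITT-VF alongside would separate virologic from other non-response at little cost

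*SAP*

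**What the plan says.** Section 10.8, Analysis 2, gives its purpose as "The impact of baseline polymorphisms on treatment outcome will be assessed as follows". For every polymorphism the SVR12 "rate will be calculated for subjects with and without the polymorphism and the 2 rates will be compared"; no test is named. Analysis 3 does the same for NS3 and NS5A polymorphisms at the key subset of positions, and "the rates with or without polymorphisms will be compared using Fisher's exact test". Both are split by arm, subtype and treatment experience. Neither states a population.

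Section 10.1 supplies the default: "All efficacy analyses will be performed on the ITT population, unless otherwise specified". Section 6.3 sets the rule for missing values: "Subjects with missing HCV RNA data in the analysis window, after imputations, will be imputed as a failure". The list of reasons for SVR12 non-response in Section 10.1 keeps on-treatment virologic failure and Relapse12 apart from reinfection, early stop without on-treatment virologic failure, missing data and other.

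Section 5.1.2 defines mITT-VF as ITT without subjects who missed SVR12 for a reason other than virologic failure. It is used in two places:
- Section 10.5, as a sensitivity analysis of the overall SVR12 rate.
- Section 10.8.1, for counts of baseline variants: "The number and percentage of subjects in the ITT and mITT-VF populations will be summarized".

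Section 10.6 gives SVR12 by baseline polymorphism in ITT.

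**The concern.** The two analyses ask whether a polymorphism present before treatment affects the result of treatment. A missed Week 12 sample, or reinfection with a different virus, carries little or no information on that, yet in ITT it weighs as much as a relapse. The SAP draws this distinction itself and has a population built on it, but does not apply that population where SVR12 rates are compared and tested.

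The trial expects very few non-responders. A comparison resting on a handful of events can be decided by one or two that have nothing to do with resistance: a real association may be hidden, or an apparent one may arise with no virologic event behind it. If the population is left open, there is also room to choose it after seeing who failed.

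**Working it through.** **1. The SAP's own figure (Section 4.3).** Inputs: SVR12 97%, N = 120, normal approximation. Half-width = 1.96 × √(0.97 × 0.03 / 120) = 0.0305, which rounds to the stated 0.031. Expected non-responders of any cause: 120 × 0.03 = 3.6, about 4.

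The SAP gives no carrier share, virologic failure rate by carrier status, non-virologic share or significance level for the resistance comparisons. Those used below are assumptions, with a two-sided 0.05 level.

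**2. Non-virologic non-response equally common in both groups.** Let v1 and v0 be the virologic failure rates in carriers and non-carriers, and m the non-virologic share.
- ITT failure rate in a group: m + (1 − m)v.
- ITT difference: (1 − m)(v1 − v0).
- mITT-VF difference: v1 − v0.

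Worked case, v1 = 10%, v0 = 1%, m = 3%: carriers 0.03 + 0.97 × 0.10 = 12.70%; non-carriers 0.03 + 0.97 × 0.01 = 3.97%; difference 8.7 points against 9.0; failure ratio 12.70/3.97 = 3.2 against 10.

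Exact Fisher power with 30 carriers and 90 non-carriers (mITT-VF group sizes reduced by m):

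| m | Difference, ITT / mITT-VF (points) | Failure ratio | Power |
|---|---|---|---|
| 2% | 8.8 / 9.0 | 4.0 / 10 | 41% / 50% |
| 3% | 8.7 / 9.0 | 3.2 / 10 | 36% / 50% |
| 5% | 8.6 / 9.0 | 2.4 / 10 | 28% / 48% |
| 10% | 8.1 / 9.0 | 1.7 / 10 | 18% / 46% |

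With a weaker effect (5% against 1%, m = 3%), power is 13% against 15%.

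**3. A few cases falling unevenly.** Assume 24 carriers and 96 non-carriers, and 2 virologic failures, both in carriers. Two-sided Fisher p-values:

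| Non-virologic cases | ITT failures (carriers; non-carriers) | ITT p | mITT-VF failures (carriers; non-carriers) | mITT-VF p |
|---|---|---|---|---|
| 1 non-carrier | 2/24; 1/96 | 0.10 | 2/24; 0/95 | 0.039 |
| 2 non-carriers | 2/24; 2/96 | 0.18 | 2/24; 0/94 | 0.040 |
| 3 non-carriers | 2/24; 3/96 | 0.26 | 2/24; 0/93 | 0.041 |
| 1 carrier, 2 non-carriers | 3/24; 2/96 | 0.054 | 2/23; 0/94 | 0.037 |
| 2 carriers, 1 non-carrier | 4/24; 1/96 | 0.006 | 2/22; 0/95 | 0.034 |

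The first three rows show masking and the last shows inflation. In the extreme, with no virologic failure at all and 2 missing-data failures that both fall in carriers (2/24 against 0/96), ITT gives p = 0.039, while mITT-VF shows 100% in both groups.

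**4. What mITT-VF would lose.** Relapse12 requires completed treatment (at least 52, 77 or 103 days in Arms A, B and C).
- A subject who stops early, is below LLOQ at the Final Treatment Visit and then rebounds is therefore placed under "Prematurely discontinued study drug with no on-treatment virologic failure" and leaves mITT-VF.
- EOT failure requires at least 36 days of drug, so an earlier stop with quantifiable RNA and no breakthrough goes the same way.
- Backward imputation uses only an unquantifiable or undetectable later value. A completer with no value in the SVR12 window whose first quantifiable RNA comes later is classed as missing.

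All three may be virologic.

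**The case against.** **ITT is defensible.** It matches the primary endpoint and the Section 10.6 subgroups. mITT-VF selects on outcome: as step 4 shows, it drops some true rebounds, while it keeps early stoppers who reach SVR12. With about 4 non-responders, losing one rebound can matter as much as adding one missing-data failure. This stands, and it rules out replacing ITT.

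**The mITT-VF rates can partly be derived already.** mITT-VF removes only non-responders, so responder counts are the same in both populations. Section 10.6 responders divided by the Section 10.8.1 mITT-VF counts give SVR12 by variant. Listings of excluded subjects, of reasons for non-response and of baseline polymorphisms are also planned. This is true for the overall groupings at the Table 9 positions. It does not reach the per-position comparisons of Analysis 2, or the Fisher tests of Analysis 3 by arm, subtype and treatment experience. Table 9 also differs from the key subset in Table 8 for NS5A.

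**The weight is low.** The analyses are exploratory, the primary and secondary endpoints have no hypothesis test, and the strata are small in either population. This stands, and it limits the point to an inexpensive improvement.

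**Stronger readings that the SAP does not support.**
- A reader might infer that every early stop is a failure. SVR12 is timed "12 weeks after the last actual dose of active study drug", so an early stopper can be a responder; only those who miss SVR12 count.
- A reader might infer that no non-virologic category can be related to a polymorphism. Step 4 shows that some can hold viral recurrence.
- A reader might infer that ITT always dilutes the effect. That needs an equal share of non-virologic cases in both groups; in small samples the shift can go either way.

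**Conclusion.** The point holds as a cheap improvement. By the Section 10.1 default, Analyses 2 and 3 rest on ITT SVR12 alone, and no planned SVR12-by-polymorphism comparison sets non-virologic non-response aside. With about 4 non-responders at the planning rate, one or two such cases can mask or create an apparent effect.

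Under equal shares of 2% to 10%, the SVR12 difference shrinks by only 2% to 10% of its size. The main loss is in the failure ratio and in power, for example 36% against 50% at m = 3% with virologic failure of 10% against 1%. Power is modest at best in both populations and the gain is small for weaker effects. All sizes depend on the assumed carrier share, failure rates, non-virologic share and 0.05 level. The p-values bear directly on Analysis 3; Analysis 2 names no test, so there the effect is on the rates shown.

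The SAP does not support calling ITT the wrong population. Each population answers a slightly different question and each can mislead with so few events, which is why both should be shown. The primary and secondary results are not affected.

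**What to change.** In Section 10.8, state that Analyses 2 and 3 are run among subjects with baseline sequence data in both ITT and mITT-VF, with the results side by side. Flag any subject excluded from mITT-VF who had viral rebound after an early stop or outside the SVR12 window, since such a case may be virologic.

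The cost is a sentence or two in the SAP and one extra set of exploratory tables. The mITT-VF population is already defined and no new data are needed. Fixing this before the primary analysis lock also prevents a choice of population once the non-responders are known.

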**Virologic failure for SVR12 = On-treatment virologic failure or Relapse12**

Only subjects who have at least one post-treatment HCV RNA value will be included in analyses of relapse. For the analysis of relapse, completion of treatment is defined as a study drug duration of 52 days or greater for Arm A, 77 days or greater for Arm B, and 103 days or greater for Arm C. If the last available post-treatment value is  $\geq$  LLOQ, then the subject will be considered a relapse (i.e., will not require confirmation).

HCV reinfection is defined as confirmed HCV RNA  $\geq$  LLOQ after the end of active treatment in a subject who had HCV RNA  $<$  LLOQ at Final Treatment Visit, along with the post treatment detection of a different HCV genotype, subtype, or clade compared with baseline, as determined by phylogenetic analysis of the NS3 or NS5A, and/or NS5B gene sequences. Reinfection in the case of the same HCV subtype is defined as a clade switch, as indicated by the lack of clustering between the baseline and post-treatment sequences by phylogenetic analysis. If phylogenetic analysis is not possible due to technical difficulties, HCV reinfection may be determined with a confirmed HCV genotype or subgenotype switch by the Versant HCV Genotype Inno-LiPA Assay v2.0 or Sanger assay.

Post-treatment relapse is defined as described earlier (**Relapse12**, **Relapse24**, **Relapseoverall**), and no genotype, subtype, or clade switch compared with baseline as determined by phylogenetic analysis of the NS3 or NS5A gene sequences. If phylogenetic analysis is not possible due to technical difficulties, the subject will be defined as having a post-treatment relapse unless an HCV genotype or subtype switch is confirmed by the Versant HCV Genotype Inno-LiPA Assay v2.0 or Sanger assay.

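### Resistance Analysis 4 labels differences between the baseline virus and a reinfecting virus as treatment-emergent, because the definition has no same-strain condition

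*SAP*

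**What the plan says.** Four parts of the SAP bear on this.

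- **Who is in Analysis 4, and what it lists (Section 10.8).** "The following analyses will be performed for subjects who do not achieve SVR 12 or SVR 24 , and who have post-baseline resistance data available". Membership depends on non-response and available sequence data, not on virologic failure. The first output is: "Listings by subject of all treatment-emergent substitutions relative to the baseline amino acid sequences will be provided for each DAA target".
- **Who is sequenced after baseline (Section 10.8).** Besides virologic failures, the SAP sequences subjects who miss SVR12 for other reasons, given as "prematurely discontinued study drug with no on-treatment virologic failure, HCV reinfection, missing SVR 12 data or other reasons", if they have a sample with HCV RNA of at least 1000 IU/mL after treatment discontinuation.
- **What counts as treatment-emergent (definitions after Table 8).** "Treatment-emergent substitution: A post-baseline substitution or an enriched polymorphism". The first component is "an amino acid substitution in a post-baseline time point sample that was not detected at baseline" (below 2%) and is seen in at least 2% of the later sequences. The second is a polymorphism present at both times whose prevalence has risen by at least 20 percentage points. Both compare the subject with his or her own baseline.
- **What reinfection is (Section 10.1).** Confirmed quantifiable HCV RNA after the end of treatment in a subject below LLOQ at the Final Treatment Visit, with "post treatment detection of a different HCV genotype, subtype, or clade compared with baseline". For the same subtype, reinfection is shown by a lack of clustering between baseline and post-treatment sequences.

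Section 6.3 adds that once another HCV treatment starts, HCV RNA values "measured on or after the start date of the new HCV treatment will be excluded from analyses". PRO values have a matching rule in Sections 6.3 and 10.9. Sequence data have none.

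**The concern.** A treatment-emergent substitution is informative only if the later virus descends from the baseline virus. In a reinfected subject, by the SAP's own definition, it does not. The comparison then measures how far apart two strains are, not what glecaprevir/pibrentasvir selected, and the label on the listing is wrong for that subject.

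Analysis 4 is where the plan describes sequence changes in subjects who did not respond. Few such subjects are expected, so a listing that mixes strain differences with changes in the original virus could mislead a reader who takes it at face value. The mix also runs against the rest of the plan. Relapse excludes reinfection, reinfection has its own category among the reasons for non-response and takes precedence over relapse and premature discontinuation (Section 10.1), and the mITT-VF population drops non-responders without virologic failure (Section 5.1.2). One Analysis 1 listing is itself limited to virologic failures. Analysis 4 makes no such separation.

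**Working it through.** The point rests on definitions, so the main check is to follow one subject through the rules.

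1. Take a subject below LLOQ at the Final Treatment Visit who later has confirmed quantifiable HCV RNA of a different subtype or clade. Under Section 10.1 this is HCV reinfection. If it occurs by the SVR12 window, the subject is an SVR12 non-responder in the reinfection category.
2. If a sample after treatment reaches 1000 IU/mL, Section 10.8 has NS3/4A and NS5A sequenced. Reinfection is named among the qualifying reasons.
3. The subject now meets both conditions for Analysis 4: SVR12 not achieved, and post-baseline resistance data available.
4. Take any position where the new strain carries an amino acid that the old strain lacked. It was below 2% at baseline and is at 2% or more afterwards, so it is a post-baseline substitution and hence treatment-emergent. Nothing in the definition asks whether the two sequences cluster. An amino acid that was a minor variant in the old strain and dominant in the new one can enter through the 20-point enrichment rule.
5. Follow-up is narrower. The Week 24 sample is included only if resistance-associated variants were detected at failure or discontinuation. Persistence is assessed only at signature positions, and a target without such variants may not be sequenced again. So some strain differences, but not all, could go on to the persistence assessment.

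**Scale.** The SAP's only design figure (Section 4.3) is reproduced: 1.96 × √(0.97 × 0.03 / 120) = 0.0305, stated as 0.031. The point does not alter it. The same inputs give the expected number of SVR12 non-responders: 120 × (1 − 0.97) = 3.6.

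The SAP gives no reinfection rate. Purely as an assumption, let 0, 1 or 2 of 3 to 5 sequenced non-responders be reinfected. Their share of the listed subjects would be:

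- of 3: 0%, 33%, 67%
- of 4: 0%, 25%, 50%
- of 5: 0%, 20%, 40%

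The range of 0% to 67% shows how sensitive a short listing is to one subject. It does not estimate how often reinfection will occur.

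**New HCV treatment.** The exclusion in Section 6.3 names HCV RNA values and PRO values. The sampling rules in Section 10.8 set no condition on new treatment, either for the first sample or for the 24-week sample. The SAP neither includes nor excludes such sequences.

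**The case against.** The strongest reply is that little harm can follow. Analysis 4 produces by-subject listings with no pooled rate, denominator or test. Section 10.7 provides a listing of subject numbers with reasons for non-response, so a careful reader can find the reinfected subject and discount the entries. Sequencing these samples is also necessary, because reinfection is decided by phylogenetic comparison. This stands as a limit on the consequences and as a defence of the data collection. It does not make the label right: the reader has to cross-reference to undo a classification that the plan itself assigns.

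Several stronger readings are tempting, but the document does not support them.

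- *Every non-responder enters Analysis 4.* A sequenced sample is required, hence HCV RNA of at least 1000 IU/mL. Reinfection is named for sequencing only among subjects who miss SVR12, so for reinfection after SVR12 the case rests on inference.
- *Samples taken after other HCV therapy are included by rule.* The SAP is silent. Because samples are selected by their HCV RNA value, the Section 6.3 exclusion can be read as barring them. The 24-week sample is the more exposed of the two, and a variant first seen then would show as new because the listing is by time point.
- *All strain differences are tracked as persistent.* Step 5 of the working shows that this is too broad.
- *The changes are reported as resistance to the study drug.* The text applies the label treatment-emergent and goes no further.
- *A quarter of the listing would be affected.* That is one assumed subject out of four, not a figure from the plan.

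**Conclusion.** The point holds as a defect in a stated rule. Section 10.8, read with the reinfection definition in Section 10.1, lists natural differences between a baseline virus and an unrelated reinfecting virus as treatment-emergent. If resistance-associated variants are found, those at signature positions are also assessed for persistence at Post-Treatment Week 24.

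The reach is limited to descriptive resistance listings. SVR12, on-treatment virologic failure and Relapse12 do not depend on them, and relapse already excludes reinfection. The size cannot be stated: it is nil if no reinfected subject is sequenced, and it could be a large part of a short listing if one or two are. The handling of sequences after the start of new HCV treatment is a separate and lesser matter, an unstated rule that should be made explicit. The correction is worth making because the plan already derives the category needed.

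**What to change.** In Section 10.8, Analysis 4:

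1. Restrict the listings of treatment-emergent substitutions, of post-baseline substitutions at signature positions and of persistence to subjects not classed as HCV reinfection under Section 10.1.
2. List reinfected subjects separately, showing polymorphisms relative to the subtype-specific reference sequence, which Section 10.8 already uses. State that the reference is that of the post-treatment virus.
3. As a secondary clarification, state that sequences from samples collected on or after the start date of new HCV treatment are excluded or flagged, in line with the HCV RNA and PRO rules.

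The cost is a few sentences, a filter on the reinfection category and on the post-treatment HCV medication data (Section 7.3), and one extra listing. No new data are needed and no efficacy analysis changes.
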